### **8.4.1 Baseline Data**

Baseline and demographic characteristics will be summarized by standard descriptive statistics (including mean and standard deviation for continuous variables such as age and standard percentages for categorical variables such as gender).

## **8.5 Subject Population(s) for Analysis**

Any subjects enrolled in the study will be included in the data.

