## **3 Investigational Plan**

### **3.1 General Design**

The study will be a two-part, pilot study to evaluate feasibility and potential needs of opioid users. The study will obtain descriptive data on the use of the DOVE device prototype. Study population will consist of study participants who use opioids either after surgical procedure or recreationally. Part 1 will consist of a one-time short questionnaire. Healthy volunteers may be enrolled in Part 2 during the device modification phase. Part 2 can consist of more than one visit. At no point during in the study will Naloxone be administered.

**Part 1** will be an exploratory study, during which will administer questionnaires to develop a better understanding of factors influencing the needs of the population. Subjects could be given the option of completing part 1 and 2 in the same day.

**Part 2** is an exploratory study. Before the start of the device phase, subjects will be surveyed for comfort and subjective concerns. They will be shown the device and asked their opinion on design and comfort. The device may undergo minor modifications in response to functionality and subject comfort, and for iterative improvements such as the shape. We will test the device on participants for comfort, fit and design, using the results to improve the device, and then test the device again. This cycle will be continued until we have optimized the prototype device. We will record subject's verbal feedback, in order to guide the process of optimizing the device. At the end of Part 2, we will have optimized the design of the device for comfort and design preference. In part 2 there may be follow-up testing. Naloxone will not be administered during the study.

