## **4 Study Population and Duration of Participation**

### **4.1 Inclusion Criteria**

- Males and Females
- 21 years of age or older
- Have used opioids for more than 3 months or will be having surgery where opioids will be administered.
- Able to provide informed consent
- Moderate to severe chronic pain treated (by prescription or illicitly) with opioids or recreation use

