### **6.1.1 Screening (Parts 1 and 2)**

- Review of Inclusion/Exclusion criteria

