### **7.4 Other Evaluations, Measures**

Part 1- Questionnaire will be given to subjects once they have been consented.

Part 2 - Participants will also be surveyed/interviewed for their subjective experience with the DOVE prototype device. The interview and questionnaire will ensure that key topics are covered, while also allowing the subject to discuss issues and experiences with the prototype device that the investigational team has not considered.

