## **12 Data Collection and Management**

Any person that meets screening criteria will be included in the data collection and analysis throughout and at the completion of the study. All clinical trial team members will receive training in responsible conduct of research using the Penn IRB standard training requirements. This will include data management and procedures for maintaining confidentiality and subject safety. The study team and sponsor will meet periodically to review the progress of the study, paying particular attention to any missing data – to ensure that all forms are completed on schedule and all data is entered, verified and available for analysis. Data will be stored in password protected files, on a secure research server with data backup performed nightly. Protected health information linking the assigned unique identifier to the subject identity will only be kept as an electronic document and will be held on the shared Penn Medicine e-drive. This document will be password protected and only study personnel will have access. Study files will be kept in a locked filing cabinet. Data will be maintained in locked files to which only authorized study personnel will have access. Data collected will be entered in RedCap, excel and/or CTMS.

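### Section 3.1 admits healthy volunteers to Part 2, the only inclusion list makes no provision for them, and nothing requires their comfort data to be shown apart from those of opioid users

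*Combined protocol and SAP*

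**What the plan says.** **Eligibility.** Section 3.1 first describes the study population as people who use opioids, after surgery or recreationally. The same paragraph then adds: "Healthy volunteers may be enrolled in Part 2 during the device modification phase". Section 4.1 is the only inclusion list, and the Study Summary repeats it. Two of its five bullets concern opioids: "Have used opioids for more than 3 months or will be having surgery where opioids will be administered" and "Moderate to severe chronic pain treated (by prescription or illicitly) with opioids or recreation use". Neither copy has a Part 2 version or mentions healthy volunteers. Section 6.1.1, whose title covers both parts, gives the screening step as "Review of Inclusion/Exclusion criteria", and Table 1 marks that review under Part 2 screening.

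**Who is analysed.** Section 8.5 states: "Any subjects enrolled in the study will be included in the data". Section 12 uses a different basis: "Any person that meets screening criteria will be included in the data collection and analysis throughout and at the completion of the study".

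**What is summarised.** Section 3.2.1 makes device comfort, tolerability and wearability the primary descriptive data. Section 8.4 aggregates survey responses, sends the qualitative primary data to charts and discussion, and plans comparisons among subgroups that it does not name. Section 3.1 describes Part 2 as a cycle of testing the device, "using the results to improve the device, and then test the device again". Section 4.5 gives Part 2 about 50 subjects, with no breakdown by type.

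**The concern.** A descriptive result is useful only if it is clear whom it describes. The device is meant for people at risk of opioid overdose. If people who do not use opioids are enrolled in Part 2 and their ratings go into one summary with those of opioid users, the primary comfort data no longer describe the target population alone. Because Part 2 feedback is used to change the prototype, the mix could also influence the design.

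There is a practical problem before any analysis. Staff who check a healthy volunteer against 4.1 would have to turn that person away, while 3.1 says that he or she may be enrolled.

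**Working it through.** The plan states no power, effect size or derived sample size on this point, so there is no figure to reproduce. The only related sum, 100 + 50 = 150 in section 4.5, is correct. The check is a comparison of sections, followed by an illustration of scale.

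**1. Can a healthy volunteer meet 4.1?** Take the term in its ordinary sense, a person without opioid-treated chronic pain or recreational opioid use.

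| Bullet in 4.1 | No surgery planned | Awaiting surgery with opioids |
|---|---|---|
| Either sex | met | met |
| Age 21 or older | can be met | can be met |
| Opioid exposure | not met | met |
| Able to consent | can be met | can be met |
| Opioid-treated chronic pain or recreational use | not met | not met |

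The first person fails 2 of 5 bullets and the second fails 1 of 5. If the term instead meant opioid users in otherwise good health, they could already qualify under 4.1 and the sentence in 3.1 would add nothing.

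**2. Does the list apply to Part 2?** Yes. Table 1 and 6.1.1 place the criteria review at Part 2 screening, and 4.5 requires Part 1 subjects to be screened again before they enter Part 2.

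**3. Are healthy volunteers in the analysis set?** Under 8.5 they are, once enrolled. Section 12 names those who meet screening criteria. If that means the 4.1 list, healthy volunteers are not among the people it names. If it means whatever 3.1 permits, they are. The wording leaves both readings open.

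**4. Must they be shown separately?** No section requires it. Section 8.4 aggregates survey answers and allows subgroup comparisons without naming the groups, so a split is allowed but not specified.

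**5. Scale, on assumed inputs only.** Let *k* of 50 Part 2 subjects be healthy volunteers, and let p_u and p_h be the proportions of opioid users and healthy volunteers who rate the device comfortable.

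Pooled proportion = [(50 − k) × p_u + k × p_h] / 50, so pooled − p_u = (k / 50) × (p_h − p_u).

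Example: k = 10, p_u = 60%, p_h = 80% gives (40 × 0.60 + 10 × 0.80) / 50 = 64%, a shift of 4 points. The documents supply none of k, p_u or p_h; only the 50 is theirs.

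| k (assumed) | Share | Shift in points if the groups differ by 10 / 20 / 30 points | Opioid users left | Exact 95% CI around an assumed 60% |
|---|---|---|---|---|
| 0 | 0% | 0 / 0 / 0 | 50 | 45.2% to 73.6% |
| 5 | 10% | 1 / 2 / 3 | 45 | 44.3% to 74.3% |
| 10 | 20% | 2 / 4 / 6 | 40 | 43.3% to 75.1% |
| 15 | 30% | 3 / 6 / 9 | 35 | 42.1% to 76.1% |
| 25 | 50% | 5 / 10 / 15 | 25 | 38.7% to 78.9% |

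The sign reverses if healthy volunteers are less comfortable than opioid users. The shift is zero if none enrol or if the two groups respond alike.

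**The case against.** The best defence is that 3.1 is a specific permission, limited to Part 2 and to device modification, and that 4.1 merely fails to repeat it. That may well be the intent. It does not remove the conflict, because the list reviewed at Part 2 screening still has no line under which such a person qualifies.

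It is also fair to say that an analysis set of all enrolled subjects is ordinary for an unpowered descriptive pilot. Section 8.5 speaks of the data in general and does not govern display. A reader might infer that it orders pooling. It does not; the gap is that no other section asks for a split.

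A reader might also infer that section 12 excludes healthy volunteers and so contradicts 8.5. That goes too far. Section 12 says who is included, excludes nobody in terms, and does not cite 4.1. It is ambiguous and should be aligned with 8.5.

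Nor do the documents support saying that nobody could tell whose feedback shaped the design. Opioid use is recorded (7.1), baseline characteristics are summarised (8.4.1), and subgroup comparisons are possible (8.4). Much Part 2 feedback is verbal, and the aggregation sentence concerns survey answers. Part 1, with about 100 subjects and no healthy-volunteer provision, also gathers opinions on design and comfort. These points limit the consequence. They do not ensure that the Part 2 primary summary keeps the groups apart.

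Last, the word healthy is used loosely: section 17 applies it to participants in both parts. The conflict therefore rests on the ordinary meaning of an undefined term.

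**Conclusion.** The point holds as a conflict in eligibility wording with a reporting gap behind it. On the ordinary meaning of healthy volunteer, 3.1 and 4.1 cannot both be followed, and nothing requires the Part 2 comfort, tolerability and wearability data to be shown by participant type. Confidence in the mismatch is high.

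The effect on results cannot be sized from the documents. With assumed healthy shares of 10% to 50% and assumed differences of 10 to 30 points, pooling would move a Part 2 comfort proportion by 1 to 15 points. Those figures only illustrate the formula. A reader might infer that the Part 2 findings will be biased, but the documents give no count of healthy volunteers, no comfort rate and no direction, and the effect may be zero. The primary objective is descriptive, so no primary hypothesis test or power claim is affected. The case for acting is that the repair is cheap and makes clear whom the summary describes.

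**What to change.** 1. Reconcile 3.1 and 4.1, with the Study Summary copy. State eligibility by part, say whether healthy volunteers may enter Part 2 and under which criteria, and define the term if they may.
2. Use one analysis-set wording in 8.5 and section 12: consented, enrolled participants, reported by part.
3. Record participant type at enrolment. Report Part 2 comfort, tolerability and wearability for opioid-using participants, with healthy volunteers in a separate row or column. Keep this descriptive and add no hypothesis test. Mark participant type on the verbal feedback too, so that the charts and discussion can keep the groups apart.

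**Cost.** Protocol wording and one flag at enrolment; opioid-use information is already collected under 7.1. No extra subjects or visits are needed. The drawback is smaller rows: *k* healthy volunteers leave about 50 − *k* opioid users. In the illustration above, going from 50 to 40 opioid users widens the interval around 60% from 45.2%–73.6% to 43.3%–75.1%, which is a small loss for a descriptive pilot. At 25 the interval is 38.7%–78.9%, so the loss becomes material if healthy volunteers make up a large share.

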## 9. Safety and Adverse Events

### 9.1 Definitions

#### 9.1.1 Adverse Event

An **adverse event** (AE) is any symptom, sign, illness or experience that develops or worsens in severity during the course of the study. Intercurrent illnesses or injuries should be regarded as adverse events. Abnormal results of diagnostic procedures are considered to be adverse events if the abnormality:

- results in study withdrawal
- is associated with a serious adverse event
- is associated with clinical signs or symptoms
- leads to additional treatment or to further diagnostic tests
- is considered by the investigator to be of clinical significance

For FDA regulated studies, the FDA defines an adverse event as the following:

Adverse event means any untoward medical occurrence associated with the use of a drug in humans whether or not considered drug related.

#### 9.1.2 Serious Adverse Event

Adverse events are classified as serious or non-serious.

A **serious adverse event** is any AE that is:

- fatal
- life-threatening
- requires or prolongs hospital stay
- results in persistent or significant disability or incapacity
- a congenital anomaly or birth defect
- an important medical event

Important medical events are those that may not be immediately life threatening, but are clearly of major clinical significance. They may jeopardize the subject, and may require intervention to prevent one of the other serious outcomes noted above. For example, drug overdose or abuse, a seizure that did not result in in-patient hospitalization, or intensive treatment of bronchospasm in an emergency department would typically be considered serious.

All adverse events that do not meet any of the criteria for serious should be regarded as **non-serious adverse events**.

### 9.2 Recording of Adverse Events

Any AE/ADE will be recorded by the Clinical Research Coordinator on the AE CRF, and signed off by the PI. Recording of adverse events will begin when the first subject is enrolled and will end when the last subject has completed all study procedures. Unanticipated adverse events (serious and non-serious) will be reported to the Penn IRB, in accordance with federal and institutional requirements.

At each contact with the subject, the investigator will seek information on adverse events by specific questioning and, as appropriate, by examination. Upon removal of the device, research personnel will evaluate for lesion at site of placement on subject via inspection and palpation. Information on all adverse events will be recorded immediately in the adverse event case report form (CRF).

All adverse events occurring during the study period (from study intervention start to end of the study) will be recorded by research personnel. The clinical course of each event will be followed until resolution, stabilization, or until it has been determined that the study intervention or participation is not the cause. Serious adverse events that are still ongoing at the end of the study period will be followed up to determine the final outcome. Any serious adverse event that occurs after the study period and is considered to be possibly related to the study intervention or study participation will be recorded and reported immediately.

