### **6.1.2 Baseline Visit**

- Signed informed consent
- Review of demographics, medical history and medications
- Questionnaire
- Dispense Investigational Product (only Part 2)
- Collect Investigational Product (only Part 2)
- Assessment of possible Adverse Events (only Part 2)

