## **7 Study Evaluations and Measurements**

### **7.1 Medical Record Review**

- Date of birth & Demographics
- Medications
- Medical/surgical history
- Information related to opioid use and history of overdose
- EPIC chart review to ensure subject meets inclusion criteria or does not meet exclusion criteria.

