## **8.1 Primary Endpoint**

For part 1 and 2 the primary objective is qualitative, only descriptive information will be obtained. The endpoint will be collection of feasibility and safety data.

As the primary objectives are descriptive and designed as a feasibility study, no power analysis will be performed. The sample size is one of convenience and limited by resources.

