### **9.4 Reporting of Adverse Events, Adverse Device Effects and Unanticipated Problems**

Investigators must conform to the adverse event reporting timelines, formats and requirements of the various entities to which they are responsible.

The minimum necessary information to be provided at the time of the initial report includes:

• Study identifier

• Study Center

• Subject number

• A description of the event

• Date of onset

	

• Current status

• Whether study intervention was discontinued

• The reason why the event is classified as serious

• Investigator assessment of the association between the event and study intervention

---	--

Additionally, all other events (unanticipated problems, adverse reactions, unanticipated adverse device effects and subject complaints will be recorded and reported with respect to institutional and federal policies.

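### The placement site is checked for lesions only when the device comes off; without a recorded look before first placement, pre-existing lesions cannot be reliably told apart from device effects

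*Combined protocol and SAP*

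**What the plan says.** The device-specific skin check is in section 9.2: "Upon removal of the device, research personnel will evaluate for lesion at site of placement on subject via inspection and palpation". The same section adds general adverse event enquiry: "At each contact with the subject, the investigator will seek information on adverse events by specific questioning and, as appropriate, by examination".

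Section 9.1.1 defines an adverse event by change: it "is any symptom, sign, illness or experience that develops or worsens in severity during the course of the study". Section 9.4 requires the initial report to give the onset date and the "Investigator assessment of the association between the event and study intervention".

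Before the device is handed over in Part 2, section 6.1.2 lists consent, "Review of demographics, medical history and medications" and the questionnaire. Adverse event assessment comes last in that list, after dispensing and collection, and applies to Part 2 only. Table 1 has the same content and no row for a skin or physical examination. The record review in section 7.1 includes "Medical/surgical history" but no item on skin or placement site. The only exclusion in section 4.2 is pregnancy.

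Section 8.1 says of both parts: "The endpoint will be collection of feasibility and safety data".

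**The concern.** The definition of an adverse event needs a before and an after, and the schedule provides only the after. When staff find a mark at removal, they have no recorded observation of the same site at placement to set against it. The error can go either way: an old lesion may be recorded as a device effect, or a lesion that the device caused or aggravated may be put down as old.

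Three features of the design give this some weight. Safety data are part of the endpoint in section 8.1. There is no comparison group to show how often such lesions occur without the device. And under section 3.1 Part 2 is iterative, with results from one round used to modify the prototype for the next, so a misread skin finding could prompt an unneeded change or let a real fault through.

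**Working it through.** **Is there a scheduled look before placement?** Each place where one could be found was checked.

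| Place | Content | Recorded state of the site before placement? |
|---|---|---|
| 4.2 Exclusion criteria | Pregnancy only | No; people with lesions can enter |
| Table 1 | Eligibility, consent, history, questionnaire, medications, dispense, collect, AE assessment | No |
| 6.1.2 Baseline visit | Same content; AE assessment listed after collection | No |
| 7.1 Medical record review | General history from records | No |
| 7.3, 7.4, 7.5 | No laboratory tests; survey and interview; oversight by the principal investigator | No |
| 9.2, general enquiry | Questions at each contact; examination at discretion, aimed at adverse events | No |
| 9.2, device check | Inspection and palpation at removal | No for the first device at a site; in part for a later one |

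On the last row: if a second prototype goes on the same site, the check made when the first came off shows the state of the skin before the second. It is a partial baseline because it covers only that site, and because section 9.2 requires adverse events to be recorded without saying that a clear site is recorded too. The gap is therefore the first placement at each site.

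**How many subjects could be affected?** The plan states no figure to reproduce: section 8.3 gives a sample of convenience with no power analysis.

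Inputs: n = 50 (approximate Part 2 enrolment, section 4.5); p = proportion with a lesion already at the placement site, **assumed** between 1% and 20% because the documents give none.

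Expected number = n × p. Chance of at least one = 1 − (1 − p)^n.

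| Assumed p | Expected, 50 × p | Chance of at least one, 1 − (1 − p)^50 |
|---|---|---|
| 1% | 0.5 | 39.5% |
| 2% | 1 | 63.6% |
| 5% | 2.5 | 92.3% |
| 10% | 5 | 99.5% |
| 20% | 10 | about 100% |

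These are subjects with a pre-existing lesion. They become misclassified subjects only where the other sources of information fail, so the expected counts are upper bounds on expected misclassification from this source.

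**Limiting case.** Suppose the device causes no lesions, p = 10%, and every old lesion is counted against the device. The correct result would be 0/50, with two-sided 95% upper limit 1 − 0.025^(1/50) = 7.1%. The reported result would be 5/50 = 10%, with Clopper-Pearson 95% interval 3.3% to 21.8%. The plan sets no safety threshold, so this alters a description and not a formal decision.

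**The case against.** The best defence is that the plan has other ways to recognise an old lesion. The subject is present throughout and can be asked. History is reviewed. Section 9.2 allows examination where appropriate, section 9.3 has the principal investigator assess each event at once, and section 9.4 asks for onset date and association in the initial report. Wear is confined to the visit (section 5.5), about 2 to 3 hours (section 4.4), with a prototype that does not function. The primary endpoints in section 3.2.1 are comfort, tolerability and opinions on wearability, so safety data have a smaller role than section 8.1 alone suggests.

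Most of this stands, and it limits the point. It does not remove it: none of these is a recorded observation of the site before placement by the staff who judge the finding at removal.

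A reader might infer four stronger things that the documents do not support:

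- *Old and new lesions cannot be told apart at all.* Some can, by the means just listed.
- *The error is permanent because there is no follow-up.* Sections 3.1.2, 6.2 and 6.4 do say there is none, but section 9.2 follows each event until it resolves, stabilises or is judged unrelated. That may settle some cases, though it cannot show how the skin looked beforehand.
- *A second prototype on the same site has no baseline.* The preceding removal check supplies a partial one.
- *Lesions are likely because of who takes part and where the device sits.* Section 3.1 allows healthy volunteers in Part 2, and section 4.1 includes surgical and prescribed opioid use. The ankle, wrist and deltoid labels in section 1.2 stand beside text on the future device and are not confirmed as the Part 2 wear sites.

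**Conclusion.** The point holds in a limited form. The plan schedules no recorded look at a site before the device is first placed there, while its adverse event definition and its safety endpoint rely on that reference. Lesions present beforehand cannot be *reliably* separated from device effects.

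The size is uncertain. With 50 subjects and an assumed prevalence of 1% to 20%, between 0.5 and 10 would be expected to have a pre-existing lesion, and the number misclassified can be anything up to that. The prevalence range is an assumption and has no source in the documents. Given brief wear of a non-functioning prototype and a descriptive objective, this is a modest weakness. It is worth correcting because the remedy is very cheap and the missing observation cannot be made once the device is on.

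**What to change.** Amend Table 1, section 6.1.2 and section 9.2 as follows.

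- The research personnel who do the removal check also inspect and palpate each intended site immediately before the device is first placed there, and record the result on the CRF, including when nothing is found.
- For a later prototype on the same site in the same visit, the preceding removal check, recorded in the same way, serves as the baseline. No extra look is needed.
- At any new visit the pre-placement look is repeated.
- Skin findings at removal are reported as new or worse relative to that record, by prototype. This applies the existing definition in section 9.1.1 and does not change it.

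Cost: one or two minutes per placement site by staff who already do the same check at removal, and one CRF field. It needs no additional visits, staff or subjects.
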